5.3 Tertiary outcomes

Outcome T3:

We will summarize the participating GPs' experiences of POCUS' influence on perceived stress, job satisfaction and burnout symptoms after the intervention and report the frequency of GPs who report POCUS to have a positive impact (Very decreased or decreased sense of stress/jobsatisfaction/sense of burnout), no impact, or a negative impact (Very increased or increased sense of stress/jobsatisfaction/sense of burnout).

6. Data collection

Data will be collected as specified in the study protocol.

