Hypothesis P1: For general practice clinics that receive a POCUS intervention the use of POCUS will increase after the intervention evaluated by comparing the number of registered reimbursement codes before the intervention to the number of reimbursement codes registered after the intervention.

(P2) To estimate the effects of a POCUS intervention for primary care clinics on the number of referrals send to secondary care specialists.

Hypothesis P2: For general practice clinics that receive a POCUS intervention the referral rate (number of referrals to hospital or specialist clinics/number of consultations) will decrease evaluated by comparing the referral rate from before the intervention to the referral rate after the intervention.

Secondary objectives:

We will estimate if POCUS leads to change in:

- S1. Number of consultations (e-mail, telephone, video, GP office, visits)
- S2. GPs' perceived stress (Cohen's 10-item Perceived Stress Scale)
- S3. GPs' job satisfaction (Warr-Cook-Wall Job satisfaction Scale)
- S4. GPs' burnout symptoms (Maslach Burnout inventory)
- S5. Healthcare costs

And in addition, we will evaluate:

- S6. Patients experiences following POCUS use
- S7. Adverse events reported by the participating GPs following the intervention
- S8. The patient pathway and the quality of selected POCUS applications used in general practice

Tertiary objectives:

- T1. GPs' experiences of job contentment before and after the intervention
- T2. GPs' experiences of POCUS use in their practice after the intervention
- T3. GPs' experiences of POCUS' influence on perceived stress, job satisfaction and burnout symptoms after the intervention.

8 Trial design

This is a stepped-wedge cluster randomized trial

[figure not shown]
Study process

This research project has been developed following the Medical Research Council's model for developing and evaluating complex interventions²¹ (Figure 1).

Reporting of this trial will follow international guidelines for reporting²² and protocols will follow the SPIRIT statement²³. Before the inclusion of the first participant, the trial protocols will be registered on clinicaltrials.gov.

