And finally, the GPs will be asked to declare on a 5-point-likerts scale if they agree or disagree that POCUS use had influenced their sense of perceived stress, job satisfaction or burnout symptoms (outcome T3).

The GP questionnaire will be distributed to participating GPs prior to the educational intervention and after the educational intervention (see Figure 2).

Patient questionnaire (secondary outcome S6)

A patient questionnaire will be delivered to all patients (≥ 18 years old) examined with POCUS, who will be able to provide an informed consent, in month 5-6 after the educational intervention (See Figure 2). The participating GPs will deliver the questionnaire to the patient after the consultation. Patients will fill out the questionnaires themselves on their own mobile devices using a QR code (or alternatively a paper questionnaire). We will use items previously developed and validated⁴⁴. The patients will be asked to declare on a 5-point-likert scale:

- If they felt informed about the purpose of the POCUS examination
- If they felt informed about the results of the POCUS examination
- If they were informed about the difference between POCUS and traditional ultrasound examinations
- If they thought the POCUS examination was a natural part of the consultation?
- If they thought the POCUS examination was disturbing in the consultation with the doctor?
- If they thought the contact between the doctor and themselves was improved or worsened?
- If they thought the ultrasound examination gave them a better or poorer understanding of their health problem?
- If they felt more thoroughly or less thoroughly examined after the ultrasound examination?
- If they felt more or less taken seriously.
- If they felt more or less secure?
- If they thought the ultrasound examination had a large or small impact on the treatment they received?
- If their confidence in the GPs assessment of their health problem had increased or decreased?
- If they thought the ultrasound examination makes the level of service at the GP's office increase or decrease?
- If they thought the ultrasound examination makes the quality in care at the GP's office increase or decrease?
- Their overall experience with the ultrasound examination performed by the physician?

The were also asked to declare on a scale from 1-10:

- How likely they were to recommend the ultrasound examination to other patients having the same health problem and the same physician? (NPT score)

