For the summarized data (S2, S3, S4, S7 and T3), we will use descriptive statistics. Data will be presented as mean (sd) and median [IQR] or n (%) and differences BEFORE and AFTER reported as differences in mean with 95% CI. For the data analysis of the GP questionnaires (S2, S3 and S4), we will include only GPs who have responded to both the BEFORE and AFTER questions related to the outcomes.

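### Outcome T3: the SAP counts positive, no and negative impact, but the item as the protocol describes it records agreement that there was an influence, without direction

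*SAP*

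**What the plan says.** The objective is worded neutrally in the protocol's list of tertiary objectives: "T3. GPs' experiences of POCUS' influence on perceived stress, job satisfaction and burnout symptoms after the intervention". It names an influence but no direction.

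Protocol section 12 (GP questionnaire) gives the measurement in one sentence. The answer format is this: "5-point-likerts scale if they agree or disagree that POCUS use had influenced their sense of perceived stress, job satisfaction or burnout symptoms (outcome T3"). Unlike T1 and T2, the item is not written out.

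SAP 5.3 gives the reporting rule. The SAP will "report the frequency of GPs who report POCUS to have a positive impact (Very decreased or decreased sense of stress/jobsatisfaction/sense of burnout), no impact". The same sentence then defines the opposite class, built from the two upper answers: "or a negative impact (Very increased or increased sense of stress/jobsatisfaction/sense of burnout").

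SAP section 6, which follows directly, adds no new T3 item: "Data will be collected as specified in the study protocol". SAP 6.2 names only the survey tool and the data extraction. SAP section 9 limits the analysis to description: "For the summarized data (S2, S3, S4, S7 and T3), we will use descriptive statistics".

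**The concern.** The two documents give T3 two response formats. One asks whether POCUS had an influence; the other needs to know which way the influence went. A GP whose stress fell and a GP whose stress rose would both truthfully agree with the protocol's statement. If that item was used, the SAP's positive and negative classes have no data behind them, and any split reported would come from whoever mapped the answers.

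T3 is the only tertiary outcome that the SAP assigns to the primary article; T1 and T2 go elsewhere. Within that article it is also the only measure in which GPs themselves attribute a change in stress, satisfaction or burnout to POCUS. S2 to S4 are before-and-after scale scores without attribution. A reader may therefore take the T3 split as the GPs' own verdict on benefit and harm.

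**Working it through.** No figure is stated for T3 and no test is planned, so there is nothing to reproduce. The check is a comparison of texts.

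1. **What each answer on the protocol's item would mean.** The item asks for agreement that an influence took place.
   - Agreement means that there was an influence in some direction. In the SAP it could be positive or negative.
   - Disagreement means that there was no influence. At best it corresponds to the SAP's no-impact class.
   - A midpoint, if the scale has one, would mean undecided. That is not the same as no impact.

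2. **What the SAP needs.** It needs five ordered answers: very decreased, decreased, no impact, increased, very increased. They are collapsed to three classes. No rule applied to the answers in step 1 recovers these, because both directions fall into the same answer.

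3. **Does the SAP replace the item?** No. Section 6 takes data collection from the protocol, and 6.2 adds no item wording. Followed as written, the plan collects the answers in step 1 and reports the classes in step 2.

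4. **Does the protocol word items directionally elsewhere?** Yes. The patient questionnaire names both poles, for example "If they thought the contact between the doctor and themselves was improved or worsened". The T2 statements carry their direction in the wording, such as more energy or more frustration. The T3 sentence does neither.

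5. **Size, with assumed shares.** The documents give no expected answers. Suppose 30% of GPs feel less stress, 10% more and 60% no change, and that everyone who felt a change agrees with the protocol's statement.
   - Protocol item: 30% + 10% = 40% agree.
   - SAP scale: 30% positive, 10% negative, 60% no impact.
   - Positive share recoverable from the protocol item: anywhere from 0% to 40%.
   - With all 200 GPs answering: 0.40 × 200 = 80 agree, and these could be 0 to 80 positive. The directional scale would give 0.30 × 200 = 60 positive and 0.10 × 200 = 20 negative.

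   The shares are invented to show the width of the gap. The logic in steps 1 to 3 does not depend on them.

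6. **A second fault in the same SAP sentence.** Job satisfaction is bracketed with stress and burnout. Read literally, decreased satisfaction counts as positive impact and increased satisfaction as negative. Aligning the response scale does not cure this, so any fix that keeps the three classes has to deal with it.

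**The case against.** The strongest reply is that the protocol sentence is a loose paraphrase. T3 is summarised, not listed item by item. The agree/disagree phrase may have been carried over from the introduction to T2. The protocol also uses the term 5-point Likert for patient items that plainly run in two directions, so the term does not exclude directional answers. The SAP, written after recruitment and randomisation, names five answers that fit a 5-point item exactly. On this reading there was always one directional item, described loosely in the protocol and more exactly in the SAP.

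Much of that stands. A reader might infer that the trial holds no directional T3 data, or that the planned split is bound to be invented. The documents do not support either inference, because the questionnaire is not among them. Nor does any section propose to treat agreement as an increase, so a claim that benefits would be reported as harms goes beyond the text.

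What the reply does not remove is the conflict. On any reading one document misdescribes the instrument, the SAP defers to the protocol on data collection, and a reader cannot tell which description is right.

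It is also fair to say that the outcome is minor. Stress, job satisfaction and burnout are measured on named scales in S2 to S4, and nothing in P1, P2, S1 or S2 to S4 changes.

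**Conclusion.** The concern holds for the item as the protocol describes it: the SAP's positive, no and negative classes cannot be derived from a statement of agreement that there was an influence. Whether data are affected depends on the wording actually sent to GPs, which the documents do not show. If the item was directional, the fault is one inaccurate sentence in Protocol 12 and no data are lost. If agree/disagree was used, the split is unsupported for every GP who answered that version, on all three constructs.

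The reversed scoring of job satisfaction in SAP 5.3 has to be corrected in both cases if the classes are kept. The consequence is limited to one tertiary, descriptive outcome. The point is worth settling before analysis because it costs almost nothing and the result is meant for the primary article.

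**What to change.** First, check the T3 item in the AFTER questionnaire as it was sent out. By Protocol Figure 2 the AFTER rounds began in May 2023, and the SAP was completed only before data collection ended, so some or all forms may already have been answered.

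- **If the item is directional:** correct Protocol 12 to state the item and its five answer options for each of the three constructs. No data are lost.
- **If agree/disagree was used:** in SAP 5.3, restrict T3 for those GPs to the share who perceive any influence, and drop the positive and negative classes for them. If a directional item is used for forms not yet sent, report the two versions separately. The version would follow cluster order, so pooling them would mix the instrument with the time of training.
- **In either case:** define the classes separately for job satisfaction, with increased as positive and decreased as negative. The SAP's present direction can stay for stress and burnout.

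The cost is a few sentences in the two documents and, at most, one change to an online form, with no extra participants or visits. The downside, if agree/disagree was used, is a weaker T3 result for the earlier responders and less comparability across clusters.

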6.1. Register-based data

From PLSP, we will receive monthly aggregated data extracted from the medical-record system in the participating GPs' clinics from October 2022 to June 2024.

Data will be delivered as monthly aggregated data in separate models:

Model 1: including all scanning-specific remuneration codes registered in the participating clinics by participating GPs and for each code the corresponding age and gender of the patient.

Model 2.1: including the total number of consultations performed in the participating GPs' clinics further specified on the type of consultation.

Model 2.2: including the total number of scanning-specific remuneration codes performed in the participating GPs' clinics further specified on the 11 different codes.

Model 2.3: including the total number of referrals sent from the participating GPs' clinics further specified on the type of referral.

Model 3.1: including the total number of consultations performed by the participating GPs further specified on the type of consultation.

Model 3.2: including the total number of scanning-specific remuneration codes performed by the participating GPs further specified on the 11 different codes.

Model 3.3: including the total number of referrals sent by the participating GPs further specified on the type of referral.

Model 4: including all scanning-specific remuneration codes registered in the participating clinics by participating GPs and for each code, the corresponding type of consultation and any referral sent on the same patient on the same date as the on the same date as the scanning-specific remuneration code was used.

From PLSP, we will also receive a time-trend estimation based on all clinics in Denmark. This estimation will show the general development in number of remuneration code and referrals from October 2022 to June 2024. This data will be used to estimate the underlying time effect which is a confounder for the analysis.

6.2. GP questionnaires

The questionnaire will be collected through SurveyXact (Rambøll, Aarhus, Denmark).

Data from the BEFORE and AFTER questionnaire will be extracted from the online survey tool as excelfiles and merged in Stata prior to the analysis.

GPs report of adverse events will be extracted from SurveyXact as excelfiles.

7. Sample size

This is a pragmatic trial where size of the sample is given by the collective agreement between PLO and the Danish Regions. We plan to make post-hoc power calculations to discuss the needed of recruitment in future similar studies. The power calculation will not be used to discuss the results in current study (5,6).

8. Safety committee

A safety committee was set up to handle all reports of adverse and suspected adverse events (AEs) and serious adverse events (SAEs). [name] headed the committee. The safety committee had the mandate to end the trial.

9. Statistical analysis

Data will be cleaned, and quality assurance will be performed to secure validity and completeness. All statistical analyses will be performed in Stata (IC version 18).

For the data analysis of P1, P2 and S1, we will receive individual GP data for the number of monthly remuneration codes (Scanning activity), referrals (Activity outside general practice) and consultations (Activity in general practice), from October 2022 to June 2024. For this period, we will also receive practice level data.

For outcomes P1, P2 and S1, we will use a linear regression mixed model adjusting for the random effect of clusters and participants, the fixed effect for steps in the analysis as well as the time trend (Data on the background population) and the effect coming from some participants' prior experience with POCUS. The time trend will be estimated from the variation in remuneration codes and referral in all GPs clinics in Denmark in the period October 2022 to June 2024.

All above mentioned analyses will be performed as complete case analyses. We will perform sensitivity analyses to (1) explore the effects of missing data using imputation of missing and (2) the time trend in our data compared to the time trend in the background population.

For the summarized data (S2, S3, S4, S7 and T3), we will use descriptive statistics. Data will be presented as mean (sd) and median [IQR] or n (%) and differences BEFORE and AFTER reported as differences in mean with 95% CI. For the data analysis of the GP questionnaires (S2, S3 and S4), we will include only GPs who have responded to both the BEFORE and AFTER questions related to the outcomes.

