Prior to the present study, we have developed and pilot tested an educational intervention in two preparatory studies. In an effectiveness study (ClinicalTrials.gov Identifier: NCT05274581), we tested if the educational intervention could lead to scanning competence and if scanning competence could be maintained over time. In a cohort study (ClinicalTrials.gov Identifier: NCT05523882), we tested the data collection tools and the implementation of the educational intervention.

Figure 1. Flowchart of the study process

OK 22: Projects included in the 2022 collective agreement between Danish Regions and The Danish Association of General Practitioners.
 OK 25: The 2025 collective agreement between Danish Regions and The Danish Association of General Practitioners, will possibly include a larger scale implementation of POCUS in general practice depending on the results of the OK22 projects.

In this SW-CRT we aim to determine the effects of our intervention by estimating the uptake of the technology by the GPs (outcome P1), change in referral rate (outcome P2), change in number of consultations delivered in primary care (outcome S1), GPs job satisfaction, level of stress, and burn-out (outcomes S2-4), as well as a health economic evaluation (outcome S5). We will also evaluate patient experiences (Outcome S6), advance events and the patient pathway following POCUS use after the introduction of the intervention.

Two-hundred GPs will participate in the study. All participants will be offered the educational intervention (Figure 2). Participants will be randomized to participate in clusters. Each cluster consists of a group of 20 GPs from the same geographical area (the five Danish regions), who receive the educational intervention at a training facility (location) at a given time. The ten clusters will receive the intervention at different timepoints (Figure 2). Hence, the study will include two clusters from each of the five Danish regions, who will receive the educational intervention at a location in the specific region: North Denmark Region (Aalborg or Sæby), Central Denmark Region (Aarhus or Herning), Region of Southern Denmark (Vejle or Odense), Region Zealand (Roskilde or Næstved) and Capital Region of Denmark (København V or Lyngby).

Figure 2. Time schedule for the SW-CRT data collection

year	2022	2022	2022	2023	2023	2023	2023	2023	2023	2023	2023	2023	2023	2023	2023	2024	2024	2024	2024	2024	

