	# GP questionnaire																				

Participating GPs are recruited from the five geographical regions in Denmark. Each geographical region is randomized to two clusters. Eligible GPs from each geographical region are randomised to be enrolled in one of the two clusters assigned to the geographical region.

Methods - Participants, interventions, and outcomes

9 Study settings

This study will be conducted in office-based general practice in Denmark

Denmark has a public health care system. However, GPs are self-employed and work in office-based general practice clinics. Almost all patients are listed with a GP for primary health care. Consultations and treatments are free-of-charge for patients. GPs act as gatekeepers for other primary care healthcare providers and secondary care specialists. GPs are paid through a combination of remuneration and fee-for-service financed through taxes²⁴. There is no fee for performing POCUS in primary care and GPs must cover expenses for the ultrasound device and their ultrasound education themselves. However, during this study GPs will have the opportunity to participate in a free-of-costs ultrasound course and following course attendance they will be able to claim a fee for performing POCUS in general practice (262,37 DKK).

Continuous medical education for GPs is centrally organized under the wings of PLO-e. PLO-e is the practical organizer of the ultrasound course delivered in this educational intervention in collaboration with the research team. Hence, PLO-e will handle the financial and practical aspects of organizing and executing the course. PLO-e has no influence on the scientific content or data collection in the study.

The study will be coordinated from CAM AAU and data will be collected by the research team at the training sessions and by the participating general practitioners in their clinics. All study data will be stored at a secure server at Aalborg University.

10 Participants

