After the teaching seminar a final post-self-test is available (a replication of the pre-self-test for teaching seminar 3) for the participants to create awareness about continuous learning process and to illustrate to what extent the learning objectives of the teaching seminar have been reached. The teachers will reach out to participants, where the test scores reveal problems or difficulties, as well as participants, where the demonstration of the scan revealed specific difficulties. These participants will be offered additional support.

Participant commitment

The educational intervention requires considerable commitments from the participants. This will be outlined in both the course description, the introduction webinar and on the first teaching seminar. Participants will have to allocate three whole days for the teaching seminar and considerable time to practice scanning skills especially during the training phase (days 8-29). Furthermore, time will be allocated to perform assignments and follow the discussion on the online platform.

To ensure this commitment, time will be spent on building group relations on the first teaching seminar. In addition, a teacher will be allocated each participant as a mentor during the learning process. The mentor will monitor individual progress in the online platform and correspond with the individual participant in the chat functions, provide feed-back on assignments and reach out to participants, who fail to be active on the online platform.

11b Criteria for discontinuing or modifying allocated interventions for a given trial participant

The trial may be discontinued for a GP in case of withdrawal of an informed consent. Hence, data collection will stop for that person at the time of withdrawal of the informed consent. Otherwise, this is an intention-to-treat study hence participants will not be excluded because of low adherence to the educational elements. However, we will collect data of the degree of participation for each participant.

11c Strategies to improve adherence to intervention protocols, and any procedures for monitoring adherence

The teacher will act as mentors for the participants and monitor participants' activity on the online platform. The teachers will monitor the activity of the participants, they are mentoring and reach out to participants, who fail to be active on the online platform or complete assignments.

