The data management will follow the rules of GDPR and the Danish Data Protection Agency. All study data will be stored on a secure server at Aalborg University. Questionnaire data will be collected using the online platform SurveyXact (Rambøll, Aarhus, Denmark). A data management agreement has been made between Rambøll and Aalborg University. At the end of the data collection, data will be moved from SurveyXact to Aalborg University's server. Register data will be collected by PLSP. Data management agreements between PLSP and Aalborg University will be made prior to the collection of data. PLSP will receive data from the different IT suppliers for the general practice clinics. Data management agreements between the IT suppliers and PLSP as well as the GP clinics and the IT suppliers already exists. For this specific study, we will develop an instruction for the GPs to incorporate in the existing data management agreement prior to the collection of data.

20a Statistical methods for analysing primary and secondary outcomes.

All statistical analyses will be performed using STATA version 17 (StataCorp, Texas, USA).

The principles of Intention-to-treat is followed in the analysis. If a GP e.g. misses one teaching seminar, we will still consider the GP has having completed the educational intervention. Data will be analyzed according to a pre-established Statistical Analysis Plan (SAP) in consultation with a statistician. For the primary outcomes (continuous data), we plan to use linear regression models adjusting for the fixed effect of time and the random effects of clusters.

Due to the nature of the study the intervention cannot be blinded to the participants, but for statistical assessment, data will be blinded as regard to time of collection and location.

20b Methods for any additional analyses (e.g. subgroup and adjusted analyses).

Sensitivity analyses and sub-analyses will be performed to explore the importance of different educational elements in the intervention and background characteristics of participating GPs. These sub-analyses will be defined in the statistical analysis plan.

20c Missing data

A sensitivity analysis will be performed in cases, where missing values are not considered random.

Data monitoring

21a Data monitoring committee (DMC).

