9.2. Handling of missing data

Throughout the study period (21 months) participating GPs will be absent from the clinic due to vacation, short illness, course participation etc. This absence will result in variation in the GPs' activity (remunerations codes and referrals). For this study, we will assume that the participants' planned absence from the clinic is comparable. Still, extraordinary absence from the clinic due to e.g. long-term illness or longer vacation will result in missing data. Missing data for participants will also occur if a participant withdraws from the study or we are unable to extract data through the medical record system from a participant in a given month. Finally, missing data will occur if the clinic does not provide individual GP data to PLSP.

We will impute for missingness in two steps.

1) If individual data on a GP is missing, we will carry over data from the practice level. This can be done if the GP has no other colleagues participating in the study and if it will be reasonable to assume an overlap between the GPs data and practice level data.

2) In other cases of missingness, we impute data based on available data separately for each of the ten clusters based on available data from the cluster and the clinic.

10. Assignment of clusters

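### P1 precision is likely overstated by a model with only cluster and GP random effects, and no planned analysis would show it; for P2 and S1 the same risk is conditional

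*SAP*

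**What the plan says.** SAP Section 9 fits P1 (scanning codes), P2 (referrals) and S1 (consultations) with a "linear regression mixed model adjusting for the random effect of clusters and participants". The fixed part has the steps, a national time trend and prior POCUS experience. Protocol Section 20a names only time and cluster effects.

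SAP Section 9 plans two sensitivity analyses, described thus: "explore the effects of missing data using imputation of missing and (2) the time trend in our data compared to the time trend". The second comparison is with national data. The only interval level in the SAP, "differences BEFORE and AFTER reported as differences in mean with 95% CI", is attached to the descriptive outcomes (S2, S3, S4, S7 and T3). Protocol Section 20b adds that "sub-analyses will be performed to explore the importance of different educational elements in the intervention and background characteristics of participating GPs"; that concerns subgroups and components, not the standard error.

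On P1, Protocol Section 9 (Study settings) says that GPs otherwise have no fee for POCUS and that "following course attendance they will be able to claim a fee for performing POCUS in general practice". Protocol Section 15 limits prior users to five per region, 25 in all.

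**The concern.** Read as random intercepts, the two random effects say three things: every GP shifts by the same amount at the intervention, month-to-month scatter is the same before and after, and any two months of one GP are equally correlated. If that is wrong, the estimate can still be sound while its standard error is too small.

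For P1 it is hard to see how it could be right. Most GPs have almost nothing to register before the course. Afterwards some will scan often and others seldom, so both the scatter and the spread between GPs rise at the crossover.

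For P2 and S1 the question is open. Each cluster is a group "who receive the educational intervention at a training facility (location) at a given time", and "time will be spent on building group relations on the first teaching seminar", so effects that differ by course group are plausible. Monthly shocks shared by a cluster, or correlation that fades over months, would act the same way.

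At stake are the width of the P1 interval and, for P2, whether a small apparent change in referrals is read as real.

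**Working it through.** **1. Inputs from the documents.** 10 clusters × 20 GPs = 200 (Protocol Section 8). 21 months, with P1 in months 3-21 (Protocol Section 18a). First course months read from Figure 2: 4, 5, 5, 6, 7, 8, 9, 10, 11, 12, with three course months each. Prior users 5 × 5 = 25, so 200 − 25 = 175 non-users. No variance, intraclass correlation, alpha or target effect is given, so there is no figure of the plan to reproduce. Everything below rests on assumed variances, and the z test is one natural reading, because SAP Section 9 names no test.

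**2. The model.** For GP *g* in cluster *i*, month *t*: y = month(t) + θ·D(i,t) + prior use + u(i) + v(g) + e. Here θ is common to all GPs and Var(e) is constant.

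**3. What P1 data would look like.** Assume a mean of 0.2 codes a month before the course (2 for prior users) and 10 after, with monthly variance m + 0.5m².
- Non-user before, m = 0.2: 0.2 + 0.5 × 0.04 = 0.22.
- Average GP after, m = 10: 10 + 0.5 × 100 = 60, about 270 times larger (60/0.22).
- SD of GP means after = CV × 10 = 5, 10 and 15 at CV 0.5, 1.0 and 1.5, around a mean rise for non-users of 10 − 0.2 = 9.8.

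The model sets the spread of rises to zero and the variance ratio to one.

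**4. Coverage of a model-based 95% interval for P1.**

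| Fit and scenario | Coverage |
|---|---|
| REML, CV 0.5 / 1.0 / 1.5 | 0.96 / 0.91 / 0.90 |
| REML, course groups differ, log SD 0.1 (CV 0.5 / 1.0) | 0.93 / 0.91 |
| REML, course groups differ, log SD 0.2 (CV 0.5 / 1.0) | 0.83 / 0.84 |
| Within-GP fit, CV 1.0 (error 11-17%) | 0.83-0.89 |
| Same, course months counted as AFTER (error 19-29%) | 0.71-0.81 |

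The jackknife with t(9) covered 0.93-0.95 in the REML scenarios, and its error was 5-7% in the within-GP fit. In every REML scenario for P1 the mean estimate lay at least 6 empirical SDs from zero.

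**5. P2 type I error at a nominal 5%.** Assume Poisson counts with mean about 42, GP SD 30%, cluster SD 5%, monthly activity CV 30%, zero mean effect and course months excluded. Let r be the mean model standard error over the empirical SD. The expected rejection rate is about 2{1 − Φ(1.96r)}.

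| Scenario | r | Formula | Simulated |
|---|---|---|---|
| Model holds | 0.99 | 5.2% | 4.8% |
| Course-group effect SD 3% | 0.97 | 5.7% | 5.6% |
| SD 5% | 0.92 | 7.1% | 7.4% |
| SD 10% | 0.71 | 16.4% | 15.1% |
| Monthly autocorrelation 0.2 | 0.88 | 8.5% | 8.3% |
| Autocorrelation 0.2 plus group SD 5% | 0.80 | 11.7% | 11.2% |

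Cluster-month noise of 3% and 5% gave 8.1% and 9.7%. Monte Carlo error is 0.5-1.0 points. A separate within-GP fit gave 4.3% if the model holds, 6.0-16.1% with group effects and 9.8% at autocorrelation 0.2.

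**6. Choice of correction with ten clusters.** Across the P2 null scenarios the jackknife with t(9) rejected 3.7-6.2%, an uncorrected cluster-robust error with z 12.1-17.6%, and one merely scaled by 10/9 with t(9) 6.7-10.4%.

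**7. Price.** The t(9) multiplier alone widens intervals by 2.262/1.960 = 1.15. P2 intervals were 18-25% wider on average. Power for a true 10% fall in referrals, with the model correct, went from 86% to 67% (19 points); the within-GP fit gave about 88% to 70% (18 points).

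**The case against.** The best defence is that this is a recognised stepped-wedge model, improved on the protocol by a participant effect, and that it is near nominal with ten clusters when its assumptions hold. Every error rate above comes from assumed variances.

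Support in the documents for group effects on P2 is thin. Curriculum, action cards and seminar structure are common to all courses, hands-on work is in groups of four, mentoring is individual, and GPs then return to their own clinics. No passage points to monthly shocks shared by a cluster. Protocol Section 20b does not mention course groups.

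Making a jackknife the main P2 inference would give up power that a fixed sample size cannot restore. The missing confidence level is a wording gap, since 95% is the only level in the SAP.

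Most of this stands for P2 and S1. A reader might infer that the P2 test is known to be anti-conservative, or that any departure matters. The documents do not support that: they give no variances, and a 3% group SD gives 5.6%, barely distinguishable from 5%. Nor do they support strong autocorrelation, because SAP Section 9.2 says that "extraordinary absence from the clinic due to e.g. long-term illness or longer vacation will result in missing data", which keeps long absences out of the observed counts.

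The defence does not reach P1. That argument needs no group effect or shared shock; it follows from the fee rule and the small share of prior users.

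**Conclusion.** The concern holds, and is firmest for P1. Codes near zero before the course and uneven use after it do not fit a common shift with constant variance. Under the assumed inputs, coverage of a model-based 95% interval is about 95% at between-GP CV 0.5 and about 83-91% at CV 1.0 or more. It is lower if course months count as AFTER, and it can be lower if course groups differ strongly. It would go too far to infer that the P1 conclusion is in doubt: the simulated rise is many standard deviations from zero, and the fee makes a rise very likely. What would be wrong is the stated precision.

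For P2 the risk is conditional: near 5% if the model holds, illustratively 6-16% if course groups differ materially, clusters share monthly shocks or correlation fades. Small departures matter little. S1 uses the same model but was not simulated. Nothing in the plan would tell the trial team which case they are in.

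**What to change.** In SAP Section 9, keep the model and the point estimates and add:
- State 95% confidence intervals for P1, P2 and S1.
- For P1, base the interval on a leave-one-cluster-out jackknife standard error, SE² = (9/10) Σ(θ₍₋ᵢ₎ − mean)², with t on 9 degrees of freedom. An equivalent small-sample-corrected cluster-robust standard error would also do.
- For P2 and S1, report the same interval as a prespecified sensitivity analysis beside the model-based one, and treat a P2 conclusion that depends on the choice as not robust.
- Do not use an uncorrected cluster-robust standard error with ten clusters.

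This should be fixed before the results are seen, so that the standard error is not chosen on them. The cost is wider P1 intervals and a little code. P1 coverage may still be slightly low (0.93) if course groups differ strongly. Making the jackknife the primary P2 inference would cost about 18-19 points of power for a 10% fall even if the model holds, so that trade-off is left to the trial team.
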